### **5.3.1.2. Values and Changes Over Time Endpoints**

#### **5.3.1.2.1. HBsAg, HBeAg, HBV DNA and ALT**

Actual values (original unit and  $\log_{10}$  transformed values) and changes from baseline ( $\log_{10}$  transformed values) over time in HBsAg, HBeAg (for participants HBeAg positive at baseline only), HBV DNA and ALT (actual values only) will be evaluated.

Change from baseline is defined as follows: value at a given time point minus baseline value.

The change from baseline value to nadir (i.e., maximum decrease for each participant) in HBsAg, HBeAg and HBV DNA will be evaluated at three intervals: on-treatment nadir, during follow-up nadir, and entire study duration nadir.

### **5.3.1.3. Time to Event Endpoints**

#### **5.3.1.3.1. Time to First HBsAg Seroconversion**

Time to first HBsAg seroconversion is defined as the number of days between the date of first study intervention intake and the date of the first occurrence of HBsAg seroconversion (i.e., the date of the first HBsAg seroconversion – the date of first study intervention intake + 1). The participants who withdrew early from the study before achieving HBsAg seroconversion or who did not achieve HBsAg seroconversion will be censored at the last available HBsAg assessment.

Time to the first occurrence of the events above will be also analyzed considering the participants who were retreated with NA before achieving the event will be censored at the date of NA retreatment.

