intervention and follow-up.	Proportion of participants with HBsAg and HBeAg seroconversion.
	Change from baseline over time in HBsAg, HBeAg, and HBV DNA.
	Time to achieve HBsAg seroclearance, HBeAg seroclearance, and/or HBV DNA <lloq.< th=""></lloq.<>
	Proportion of participants with HBeAg, HBsAg, and HBV DNA levels and/or changes from baseline below/above different cut-offs.
To evaluate the frequency of virologic breakthrough.	Proportion of participants with virologic breakthrough.
To evaluate the efficacy of NA re-treatment in participants who meet the criteria for NA re-treatment.	Proportion of participants who reach HBV DNA undetectability after re-start of NA treatment during follow-up.
• To evaluate the pharmacokinetics (PK) of JNJ-3989 (ie, JNJ-3976 and JNJ-3924) and optionally of JNJ-6379, NA and/or PegIFN-α2a.	Ontionally PK parameters of INI-6379 NA
Exploratory	

 
To identify baseline and on-treatment markers associated with efficacy.
 
	
 
Association of baseline characteristics and baseline/on-treatment viral blood markers (such as age, and baseline/on-treatment HBsAg levels) with selected efficacy variables.
 

To explore changes in the severity of liver disease.	Changes in fibrosis (according to Fibroscan liver stiffness measurements) at end-of-study intervention (EOSI) and end of follow-up versus baseline.
To explore efficacy of the study intervention in terms of changes in HBV RNA and HBcrAg levels.	2
To explore the impact of study intervention on participants' physical and emotional	• Changes over time in score on the Short Form 36 version 2 (SF-36v2).
functioning, and health-related quality of life using patient-reported outcomes (PROs) during study intervention and follow-up.	Changes over time in score on the Hepatitis B Quality of Life (HBQOL) Instrument.
	Changes over time in the 5-Level EuroQol 5-Dimension (EQ-5D-5L) Visual Analog Scale (VAS) score and Index score.

Amendment 7

Objectives	Endpoints
	Changes over time on the Patient Global Impression of Change (PGIC).
• To explore the relationship between plasma PK parameters (JNJ-3976, JNJ-3924, and optionally JNJ-6379, NA and/or PegIFN-α2a) and selected pharmacodynamic (PD) parameters of efficacy and/or safety, as applicable.	• Relationship between various plasma PK parameters (JNJ-3976, JNJ-3924, , and optionally JNJ-6379, NA and/or PegIFN-α2a) and selected efficacy and/or safety endpoints, as applicable.

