The blood markers (such as HBsAg, HBeAg, HBV DNA, and ALT) during study intervention and follow-up will also be summarized by cohort over time and plotted. The proportion of participants with virologic breakthrough (on-treatment) and the proportion of participants with (sustained) reduction, suppression, and/or seroclearance during follow-up considering single and multiple markers (such as HBsAg, HBeAg, HBV DNA, and ALT) and various thresholds for the viral biomarker levels and/or changes from baseline will be summarized by cohort. The proportion of participants with HBsAg and HBeAg seroconversion will be tabulated by cohort. Descriptive statistics on values and changes from baseline over time in HBsAg, HBeAg and HBV DNA will be summarized by cohort.

The time to achieve first HBsAg and HBeAg seroclearance post randomization will be summarized, respectively, based on Kaplan-Meier estimates in tables and graphs.

The proportion of participants with HBsAg, HBeAg, and HBV DNA levels and/or changes from baseline below/above different cut-offs, will be analyzed as appropriate by cohort and over time. The proportion of participants who reach HBV DNA undetectability after re-start of NA treatment will be summarized by cohort.

Graphic data displays will also be used to summarize the efficacy data by cohort and over time.

Missing data for secondary and exploratory endpoints may be handled with a similar approach as the primary endpoint, adjusting the analysis window (e.g.,  $\pm 12$  weeks) for the specific time point as appropriate. If no data is available in the appropriate window for the given time point of interest then the imputation to non-response will be used in case of binary variables, and only observed cases for continuous variables.

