
 
To evaluate efficacy of the study intervention as measured by blood markers (such as HBsAg, HBeAg, HBV DNA, and alanine aminotransferase [ALT]) during study intervention and follow-up.
 
	
 
Proportion of participants with (sustained) reduction, suppression, and/or seroclearance considering single and multiple markers (such as HBsAg, HBeAg, HBV DNA, and ALT).
 
Proportion of participants with HBsAg and HBeAg seroconversion.
 
Change from baseline over time in HBsAg, HBeAg, and HBV DNA.
 
Time to achieve HBsAg seroclearance, and/or HBV DNA <LLOQ.
 
Proportion of participants with HBeAg, HBsAg, and HBV DNA levels and/or changes from baseline below/above different cut-offs.
 

 
To evaluate the frequency of virologic breakthrough.
 
	
 
Proportion of participants with virologic breakthrough.
 

 
To evaluate the efficacy of NA re-treatment in participants who meet the criteria for NA re-treatment.
 
	
 
Proportion of participants who reach HBV DNA undetectability after re-start of NA treatment during follow-up.
 

 
To evaluate the pharmacokinetics (PK) of JNJ-3989 (ie, JNJ-3976 and JNJ-3924) and optionally of JNJ 6379, NA and/or PegIFN-<math>\alpha</math>2a.
 
	
 
PK parameters of JNJ-3976 and JNJ-3924.
 
Optionally, PK parameters of JNJ 6379, NA and/or PegIFN-<math>\alpha</math>2a compared to historical data.
 

Exploratory	

 
To identify baseline and on-treatment markers associated with efficacy.
 
	
 
Association of baseline characteristics and baseline/on-treatment viral blood markers (such as age, and baseline/on-treatment
 

Objectives	Endpoints
	HBsAg levels) with selected efficacy variables.

 
To explore changes in the severity of liver disease.
 
	
 
Changes in fibrosis (according to Fibroscan liver stiffness measurements) at end-of-study intervention (EOSI) and end of follow-up versus baseline.
 

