### **5.3.1.1.5. HBsAg and HBeAg Seroconversion**

Seroconversion of HBsAg is defined as having achieved HBsAg sero clearance (as quantitative HBsAg level <LLOQ) and appearance of anti-HBs antibodies, defined as a baseline anti-HBs (quantitative) <LLOQ and a post-baseline assessment  $\geq$ LLOQ.

Seroconversion of HBeAg is defined as having achieved HBeAg sero clearance (as quantitative HBeAg level < LLOQ) and appearance of anti-HBe antibodies, defined as a baseline anti-Hbe antibodies (qualitative) with a "NEGATIVE" result and a post-baseline assessment with "POSITIVE" result.

The seroconversion will only be assessed at the time points when the anti-HBs or anti-HBe antibodies assessment is available.

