### 5.3.2.3.1. Time to First HBsAg Seroconversion

Time to first HBsAg seroconversion will be summarized. The Kaplan-Meier method will be used to estimate and plot the cumulative incidence. The median time with 90% CI will be estimated using Kaplan-Meier method.

In addition, the number and percentage of participants who had an event or were censored will be reported.

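### SAP 5.3.1.3.1 and 5.3.2.3.1 name HBsAg seroconversion as the time-to-event endpoint, while the protocol and the rest of the SAP name HBsAg seroclearance; the two sections need aligning.

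*SAP*

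**What the plan says.** **Protocol.** The objectives table (synopsis and Section 3) lists "Time to achieve HBsAg seroclearance, HBeAg seroclearance, and/or HBV DNA" below LLOQ among the secondary endpoints. Section 9.4.1.2 adds that "The time to achieve first HBsAg and HBeAg seroclearance post randomization will be summarized" by Kaplan-Meier estimates. Appendix 1 defines seroclearance and seroconversion as separate terms.

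**SAP objectives.** SAP 1.1 keeps "Time to achieve HBsAg seroclearance, and/or HBV DNA" below LLOQ.

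**SAP operative sections.** SAP 5.3.1.3.1 reads: "Time to first HBsAg seroconversion is defined as the number of days between the date of first study intervention intake". SAP 5.3.2.3.1 reads: "Time to first HBsAg seroconversion will be summarized. The Kaplan-Meier method will be used to estimate and plot the cumulative incidence". The word seroconversion appears six times in the first section (heading, definition, event date, formula and both censoring conditions) and twice in the second (heading and summary sentence). Participants without the event are censored at their last HBsAg assessment.

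**SAP definitions.** Section 5.3.1.1.3 defines seroclearance as quantitative HBsAg below LLOQ. Section 5.3.1.1.5 defines seroconversion as that "and appearance of anti-HBs antibodies, defined as a baseline anti-HBs (quantitative) <LLOQ and a post-baseline assessment" at or above LLOQ, assessable only at time points with an antibody result.

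**The concern.** The two events are not interchangeable, and both have complete definitions in the SAP. A programmer working from 5.3.1.3.1 would find a usable definition of seroconversion in 5.3.1.1.5 and could build the variable without anything signalling a problem. No other SAP section defines a time-to-seroclearance variable.

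On that literal reading:
- a participant who loses HBsAg without developing anti-HBs is censored as event-free;
- a participant with anti-HBs at or above LLOQ at baseline can never have the event;
- the remaining events are dated on a sparser antibody schedule.

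The resulting curve could only show HBsAg loss as less frequent and later than it was, or at best the same. It would stand where the protocol's endpoint should be.

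**Working it through.** The plan states no figure for this endpoint, so there is none to reproduce. The check compares wording and definitions, then counts scheduled visits.

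**1. Which event each place names**
- Seroclearance: Protocol objectives table; Protocol 9.4.1.2; SAP 1.1; the SAP contents titles for 5.3.1.3.1 and 5.3.2.3.1; the Amendment 2 rationale, which keeps time to first HBsAg seroclearance as one of only two time-to-event endpoints of interest.
- Seroconversion: the headings and body text of SAP 5.3.1.3.1 and 5.3.2.3.1, 6 + 2 = 8 uses.
- No SAP amendment entry records a switch from one to the other.

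**2. What the definitions imply**
Seroconversion requires seroclearance plus an anti-HBs change from below LLOQ to at or above LLOQ. Its events are therefore a subset of seroclearance events. For any participant, time to seroconversion is at least time to seroclearance.

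**3. Scheduled post-baseline sampling, Cohort 2 (Schedule of Activities 1.3.1 and 1.3.2)**
- Quantitative HBsAg: 11 induction visits (Weeks 2 to 36) + 5 consolidation + 13 follow-up = 29.
- Footnote d to 1.3.2 waives 7 follow-up visits (Weeks 8, 16, 20, 28, 32, 40, 44) for participants who did not complete NA at FU Week 2 or who restarted it, if HBV DNA and ALT are stable: 29 − 7 = 22.
- Anti-HBs: Weeks 24 and 36, Consolidation Week 12, FU Weeks 4, 12, 24, 36 and 48 = 8. None of these is waived.
- The first scheduled visit able to register an event is Week 2 for seroclearance and Week 24 for seroconversion. An early-withdrawal visit also collects anti-HBs and could fall sooner.

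**4. Delay from the schedule alone**
Assume, favourably to the literal text, that anti-HBs appears exactly when HBsAg is lost. The delay is the week of the next anti-HBs visit minus the week of the HBsAg visit.
- Largest: Week 24 − Week 2 = 22 weeks. Smallest: 0, where both are sampled.
- Summed over visits: induction 112, consolidation 28, follow-up 42; 182 / 29 = 6.3 weeks per visit.
- The 7 waivable visits contribute 4 + 8 + 4 + 8 + 4 + 8 + 4 = 40, so without them (182 − 40) / 22 = 6.5 weeks.

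These are unweighted averages over visits. They describe the grid and do not predict the delay, which depends on when losses occur.

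**5. What cannot be computed**
The documents give neither the expected number of HBsAg losses, nor the share without anti-HBs, nor the number with baseline anti-HBs at or above LLOQ. The counts in step 3 do not describe Cohort 1, where induction may run to Week 60, although SAP 5.3.2.3 analyses all treated participants.

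**The case against.** The strongest reply is that the SAP plainly means seroclearance. Its objectives table, its contents titles for these very sections and its Amendment 2 rationale all say so, and censoring at the last HBsAg assessment fits that event and ignores anti-HBs. A contents list normally repeats its headings, so the mismatch may be a wording slip or a text-conversion error. The body headings of 5.3.1.1.3, 5.3.1.1.4 and 5.3.2.1.2 show the neighbouring word split in two.

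Most of this stands. A reader might infer that the sponsor deliberately replaced the protocol endpoint, or that the SAP as a whole plans a seroconversion analysis; the documents do not support either reading. A conversion error cannot be excluded until the PDF is checked. A split word is, however, a different defect from a consistent substitution in eight places.

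The consequences are also limited. SAP 1.3 sets no formal hypothesis and SAP 5.1.1 plans no formal test. Seroclearance proportions are still evaluated over time (SAP 5.3.1.1.3 and 5.3.2.1.2; Table 3). A reader might infer that HBsAg loss would go unreported, but its frequency and visit-level timing would remain visible there. The 29-visit count is also a maximum: the SAP Amendment 4 log says only one participant met the NA completion criteria and stopped NA at Consolidation Week 12, so 22 is the required count for nearly everyone if their values are stable.

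What the reply does not remove is that outputs are normally programmed from definition and method sections, and those name the wrong event.

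**Conclusion.** The point holds as an internal contradiction. The two operative SAP sections, in the text as supplied, name a stricter event than the protocol and the rest of the SAP, and the intended event is clear.

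On a literal reading, losses without new anti-HBs become censored observations, some participants cannot have the event, and event dating moves from 22 to 29 scheduled visits to 8. The direction is certain from the definitions, because seroconversion cannot be more frequent or earlier than seroclearance. The size is unknown.

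The issue is confined to one descriptive secondary endpoint. The primary endpoint, the sample size and the seroclearance proportions over time do not depend on it. It should be corrected because correction is free, but it is not a critical defect. The conclusion assumes that the source PDF carries the same wording; if it reads seroclearance, the point falls away. Whether the programmed variable follows the body text cannot be told from the documents.

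**What to change.** 1. Confirm the wording of SAP 5.3.1.3.1 and 5.3.2.3.1 in the source PDF.
2. If it reads seroconversion, replace it throughout both sections (headings, definition, event date, formula, censoring conditions and Kaplan-Meier text) with: seroclearance (quantitative HBsAg <LLOQ, Section 5.3.1.1.3).
3. Keep censoring at the last available HBsAg assessment, which already suits that event.
4. Check that the derived-variable specification uses the HBsAg-only event.
5. If time to seroconversion is also of interest, add it as a separate exploratory variable censored at the last anti-HBs assessment.

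The cost is a wording edit and a check of one derived variable, with no new data. SAP Table 3 schedules time-to-event outputs only for the final analysis, so the interim and primary analysis outputs are not affected.

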#### **5.3.1.3.2. Time to First HBV DNA < LLOQ**

Time to first HBV DNA < LLOQ is defined as the number of days between the date of first study intervention intake and the date of the first occurrence of HBV DNA < LLOQ (i.e., the date of the first HBV DNA < LLOQ – the date of first study intervention intake + 1). The participants who withdrew early from the study before achieving HBV DNA < LLOQ or who did not achieve HBV DNA < LLOQ will be censored at the last available HBV DNA assessment.

Time to first HBV DNA < LLOQ will be also analyzed considering the participants who were retreated with NA before achieving HBV DNA < LLOQ will be censored at the date of NA retreatment.

### **5.3.2. Analysis Methods**

Statistical analyses of all secondary endpoints will be performed by cohort using Treated analysis set. The selected secondary endpoints efficacy analyses will use combining the data from participants who received PegIFN- $\alpha$ 2a but not JNJ-6379 in Cohort 1 with data of Cohort 2, the PegIFN- $\alpha$ 2a ITT analysis set will be used. If applicable, additional statistical analyses (descriptive statistics and spaghetti plots) may be added for each of the following subgroups: participants who

received at least one dose of JNJ-6379 and an induction phase duration of  $\leq 36$  weeks, participants who received at least one dose of JNJ-6379 and an induction phase duration  $> 36$  weeks, participants who never received JNJ-6379. The mTreated and mPegIFN- $\alpha$ 2a ITT will be used if relevant difference between the sets exists (see Section 2.3).

### **5.3.2.1. Binary Outcomes**

The number and proportion (%) of participants achieving the endpoints will be summarized. The associated 90% CI may also be included.

#### **5.3.2.1.1. NA Treatment Completion Criteria**

##### **5.3.2.1.1.1. NA Treatment Completion Criteria During the Study**

The count and proportion of participants who met the NA treatment completion criteria (as defined Section 5.3.1.1.2.1) and at any time during the study, regardless of the treatment duration, will be summarized by cohort.

Starting at consolidation Week 12, the incidence of participants who did not meet the NA treatment completion criteria will be summarized by cohort and at each timepoint during the study, accompanied by the distribution of each of the 4 criteria that is not met. The NA treatment completion criteria are based on a threshold for the laboratory tests of ALT, HBV DNA, HBeAg and HBsAg as defined in Section 5.3.1.1.2.1.

The count and proportion of participants who met the NA treatment completion criteria (as defined in Section 5.3.1.1.2.1) at any time during the FU phase, regardless of the treatment duration, will be summarized by cohort. All of NA treatment completion criteria will be checked based on clinical laboratory tests in FU phase.

A listing including the participants who do not meet the NA completion criteria at consolidation Week 12, and the NA completion criteria will be generated. A bar chart for including the participants who do not meet the NA completion criteria at consolidation Week 12 will be generated.

##### **5.3.2.1.1.2. NA Re-Treatment Criteria and Monitoring After Stopping of NA**

The number and proportion of participants who meet the criteria for NA re-treatment at any time during FU will be summarized descriptively by cohort. Only the subset of ITT participants who meet the NA treatment completion criteria at any time during the study and actually stop NA treatment will be included in the analysis (as defined in Section 5.3.1.1.2.2).

The proportion of participants who actually re-started NA treatment and monitoring after stopping of NA on the basis of the ‘Study Drug Administration for NA’ CRF page will be summarized separately over time by cohort.

In addition, the proportion of participants who met the above criteria according to the flag on the CRF page of 'NA Re-treatment Criteria Assessment' during the follow-up phase will be summarized over time by cohort.

A cross-tabulation of participants who actually re-started NA treatment (re-started/not restarted) versus participants versus participants who met the above criteria (met/not met) will be presented over time.

A listing including all participants who meet the NA re-treatment criteria and monitoring after stopping of NA will be generate. This listing will also include information whether they actually re-started NA treatment (re-started/not restarted).

### **5.3.2.1.2. HBsAg Sero clearance**

The proportion of participants achieving HBsAg seroclearance over time will be summarized by cohort and analysis phase. Separate analyses will be performed for participants who completed treatment as planned (at the end of consolidation phase), and regardless when treatment was stopped.

The proportion of participants with HBsAg seroclearance at the end of consolidation treatment will be tabulated by cohort.

The proportion of participants with HBsAg seroclearance will be evaluated at all off-treatment time points, respectively, after stopping all study interventions and without restarting NA treatment. In an additional summary, these proportions will be calculated with the denominator including only on those participants who have reached the off-treatment timepoint, and have stopped all interventions including NA and have not restarted NA prior to the timepoint of interest.

### **5.3.2.1.3. HBsAg and HBeAg Seroconversion**

The number and proportion of participants who achieve HBsAg and HBeAg seroconversion will be summarized descriptively by cohort and analysis phase over time.

For participants achieving HBsAg seroconversion, descriptive statistics will be calculated for the level of anti-HBs antibodies at the timepoint when achieving the HBsAg seroconversion by cohort. In an additional summary, the level of anti-HBs antibodies at the specific timepoint (i.e., end of consolidation, FU Week 24, FU Week 36 and FU Week 48) will be summarized for the subset of the participants achieving HBsAg seroconversion at any time before or at that given timepoint by cohort.

### **5.3.2.1.4. Suppressed HBV DNA**

The proportion of participants achieving HBV DNA <LLOQ (overall and separately for HBV DNA detectable and HBV DNA TND) will be summarized by cohort and analysis phase over time.

The proportion of participants with HBV DNA<LLOQ (overall and separately for HBV DNA detectable and HBV DNA TND) will be evaluated at each of the off-treatment time points,

respectively, after stopping all study interventions and without restarting NA treatment. In an additional summary, these proportions will be calculated with the denominator including only on those participants who have reached the off-treatment timepoint, and have stopped all interventions including NA and have not restarted NA prior to the timepoint of interest.

The proportion of participants who reach HBV DNA <LLOQ (overall and separately for HBV DNA detectable and HBV DNA TND) after restart of NA treatment during follow-up will also be tabulated by cohort.

The number of occurrences each subject has HBV DNA<LLOQ (overall and separately for HBV DNA detectable and HBV DNA TND) will be determined and summarized by cohort using frequency distributions and descriptive statistics. Additionally, the number of occurrences will be displayed graphically.

